8.2. Setting

Population

This study will use data from a large, commercially available, database of adjudicated medical and pharmacy claims from closed-network health insurers in the US. The population in this database is broadly representative of those in the US covered by commercial, managed Medicare, or managed Medicaid health plans⁴⁰.

Care setting

Medical claims in this database represent all care settings (e.g., physician office, hospital outpatient, hospital inpatient) and all health care provider services (e.g., evaluation and management, diagnostic procedures, nonsurgical procedures, surgical procedures) commonly reimbursed by third-party payers. Pharmacy claims in this database are primarily from retail pharmacies.

Time period

The study will examine data from September 1, 2019, to March 31, 2023. The first date of rimegepant initiation during this period will be defined as the index date.

The pattern of opioid and barbiturate utilization will be assessed 180 days before (pre-index) and 180 days after (post-index) the index date. The study baseline will be defined as the pre-index period plus the index date. Each outcome measure will be calculated separately for 12 consecutive 30-day periods (study months), starting 6 months before and ending 6 months after the index date.

Baseline clinical characteristics and comorbidities will be assessed based on diagnosis codes in inpatient or outpatient medical claims. Medication use will be identified from National Drug Codes (NDC) in pharmacy claims or Healthcare Common Procedural Coding System (HCPCS) codes in medical claims. Migraine medications will be categorized as those intended for acute treatment, prevention of, or both, based on their common usage for migraine.

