8.2.1. Inclusion Criteria

Patients must meet all of the following inclusion criteria to be eligible for inclusion in the study:

- 1. Have an index ("first") prescription fill for rimegepant between March 1, 2020, and October 1, 2022; the date of this index fill defines the index date
 - a. The end date of cohort eligibility is 6 months prior to the end of data availability to ensure sufficient follow-up for all patients prior to the end of data availability. For the 12-month sensitivity analysis, the end of cohort eligibility will be April 1, 2022.
- 2. Have an index fill quantity for rimegepant of 8 tablets (ie, intended use for acute treatment of migraine).
- 3. Have ≥ 180 days of rimegepant use from index date to last fill date +30 days
 - a. The period of rimegepant use is measured as the number of days from the index date, or first observed rimegepant fill, to the last observed rimegepant fill date +30 days.
- 4. Be \geq 18 years of age on the index date

- 5. Have ≥180 days of continuous enrollment in commercial health plans with both medical and pharmacy benefits prior to and following the index date, defined as the pre-index period and post-index period, respectively
- 6. Have a diagnosis of "migraine" (ICD-10-CM code: G43.xx) at *any point* during the pre- or post-index periodsHave ≥1 prescription fill during the pre-index period for one of the following drugs of interest: opioids, barbiturates (butalbital), alprazolam, rescue inhalers, or statins

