- b) Subgroup analysis #2: Identify individuals form the opioid use group having potentially problematic opioid use. This subgroup is a composite of problematic opioid use defined in two ways. Patients meeting either measurement definition will be included.
 - i. The first method will identify individuals in the cohort with ≥ 3 opioid prescriptions during the pre-index period.
- 6. The second method will calculate quartiles of opioid dose in MMEs and identifies individuals within the fourth quartile (76th to 100th percentile) during the pre-index period.
 - c) Sensitivity analysis #1: Increase the duration of the pre-index and post-index periods from 180 days each to 360 days each.
 - d) Sensitivity analysis #2: Exclude all patients having a major surgical procedure or injury diagnosis at any point during the study period.

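### The 360-day sensitivity analysis moves only the end of cohort eligibility, so index dates from 1 March to 25 August 2020 lack a full look-back within the stated data window

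*Protocol*

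**What the plan says.** Section 8.2 (Time period) sets the data window: "The study will examine data from September 1, 2019, to March 31, 2023". Criterion 1 in section 8.2.1 requires an index "prescription fill for rimegepant between March 1, 2020, and October 1, 2022". For the main analysis, section 8.2 states: "The pattern of opioid and barbiturate utilization will be assessed 180 days before (pre-index) and 180 days after (post-index) the index date".

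Section 8.7.1 then defines sensitivity analysis #1 as follows: "Increase the duration of the pre-index and post-index periods from 180 days each to 360 days each". Only criterion 1a adapts the cohort dates to it: "For the 12-month sensitivity analysis, the end of cohort eligibility will be April 1, 2022". The reason given for the end-date rule concerns follow-up alone: "The end date of cohort eligibility is 6 months prior to the end of data availability to ensure sufficient follow-up for all patients". Nothing is said about the start of eligibility or about the look-back.

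Criterion 5 sets the enrollment requirement: "Have ≥180 days of continuous enrollment in commercial health plans", with medical and pharmacy benefits, "prior to and following the index date, defined as the pre-index period and post-index period, respectively". No 360-day version is given.

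**The concern.** The protocol adjusts one end of the index window for the longer periods and not the other. The gap between the start of data and the first index date is just long enough for a 180-day look-back, so it cannot hold 360 days. Early initiators would have a complete 360-day post-index period and an incomplete pre-index period.

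Section 8.7.1 plans crude counts per 30-day window, summed to pre- and post-index totals and compared as a percent change. It states no adjustment for observed time. If unobserved days enter as days without fills, the pre-index totals for fills, quantity and days supplied are too low, and a real reduction would look smaller or absent. Section 8.7.1 offers this analysis as a test of robustness, so a shortfall built into its dates weakens what it can show.

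**Working it through.** **Inputs**
- Data window: 1 Sep 2019 to 31 Mar 2023 (section 8.2).
- Index dates, main analysis: 1 Mar 2020 to 1 Oct 2022 (section 8.2.1, criterion 1).
- Index dates, sensitivity analysis #1: end moved to 1 Apr 2022 (criterion 1a); no new start given.
- Period length: 180 days each side (section 8.2); 360 days each side in sensitivity analysis #1 (section 8.7.1).

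**Main analysis, both ends**
- Start: 1 Mar 2020 − 180 days = 3 Sep 2019, inside the data. From 1 Sep 2019 to 1 Mar 2020 is 182 days.
- End: 1 Oct 2022 + 180 days = 30 Mar 2023, inside the data.

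**Sensitivity analysis #1, the end that was moved**
- 1 Apr 2022 + 360 days = 27 Mar 2023, inside the data. The protocol's new end date reproduces.

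**Sensitivity analysis #1, the start that was not moved**
- 1 Mar 2020 − 360 days = 7 Mar 2019.
- Days before the data window for that index date: 360 − 182 = 178, which is 178/360 = 49% of the look-back.
- First index date with a full look-back: 1 Sep 2019 + 360 days = 26 Aug 2020.
- Affected index dates: 1 Mar to 25 Aug 2020 = 178 days. Eligible index dates: 1 Mar 2020 to 1 Apr 2022 = 762 days. Share: 178/762 = 23%. Unaffected: 762 − 178 = 584 days.

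**Size if affected patients stay in with unobserved days counted as no use**

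Assumptions: index dates uniform over the 178 affected days, a constant fill rate, and the same average use in affected and other patients.
- The shortfall runs from 178 days down to 1 day, so the mean is (178 + 1)/2 = 89.5 days, or 89.5/360 = 24.9% of the look-back.
- With a share *w* of the cohort affected, pre-index totals are understated by *w* × 0.249. The apparent change when true use is flat is 1/(1 − *w* × 0.249) − 1.

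| Share affected *w* (assumed) | Pre-index total understated by | Apparent increase under constant use |
|---|---|---|
| 5% | 1.2% | 1.3% |
| 10% | 2.5% | 2.5% |
| 23% (uniform over all 762 days) | 5.8% | 6.2% |
| 30% | 7.5% | 8.1% |

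The protocol gives no distribution of index dates, so *w* is an assumed range. The extreme single case is an index date of 1 Mar 2020: 182/360 = 51% of the look-back is observed, and constant use would appear as 360/182 − 1 = +98%. That figure belongs to one index date and does not describe the cohort.

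**Size if affected patients drop out**

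There is no understatement. The index window becomes 26 Aug 2020 to 1 Apr 2022 (584 of 762 dates), a start date that the protocol does not state.

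**The case against.** A reader might infer that the protocol as written necessarily understates pre-index use. The document does not support that, for four reasons.

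1. Criterion 5 defines the enrollment spans as the pre- and post-index periods. Since sensitivity analysis #1 lengthens those periods, the enrollment requirement can be read as rising to 360 days with them. If enrollment is seen only from 1 September 2019, early initiators are then excluded and no window is truncated. This reading is fair and makes the bias conditional. It does not remove the gap, because the cohort start would then move by almost six months unannounced. The understatement also remains if earlier enrollment is visible but earlier claims are not used.
2. The date 1 September 2019 bounds the data the study will examine. Nothing says the database itself begins there, so an earlier extract may be possible. Even so, the protocol states no earlier start for this analysis, and section 8.6 plans a single extract under the stated timeframe.
3. The mixed models use repeated measurements. If unobserved 30-day windows were treated as missing, modelled rates need not be biased, although raw totals would be. Discontinuation depends only on post-index fills, and average dose is not a total, so a short look-back does not mechanically lower either. The protocol does not say how unobserved windows are handled.
4. Operational logic is deferred to a data dictionary listed in Annex 1, which may settle the matter. It cannot, however, correct dates that criterion 1a sets for this analysis and leaves incomplete.

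A reader might also infer a threat to the main finding. There is none: the 180-day analysis fits its data at both ends, and any bias here runs against showing a reduction, so it cannot create false support for one.

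**Conclusion.** The inconsistency is real and confined to sensitivity analysis #1. The stated dates cannot supply the stated look-back for 178 of 762 eligible index dates, by up to 178 days. This follows from the protocol's own dates and needs no assumption beyond taking the section 8.2 data window as it stands.

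What happens next depends on an unstated rule. Under a literal 180-day enrollment requirement, with unobserved days counted as no use, pre-index fills, quantity and days supplied are understated by roughly 1% to 7.5% at cohort level, giving a spurious increase of about 1% to 8% if 5% to 30% of patients are affected. Slow uptake after launch would put the figure toward the low end. Under a 360-day enrollment requirement visible only from 1 September 2019, nothing is understated, but the cohort differs from the one criterion 1a describes, and a difference from the 180-day result could reflect the changed cohort as well as the longer window.

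Two programmers following this text could build different cohorts. The point warrants correction, but it ranks below an essential change because the primary analysis is untouched.

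**What to change.** Extend criterion 1a to read, for example: *For the 12-month sensitivity analysis, cohort eligibility runs from August 26, 2020, to April 1, 2022, with at least 360 days of continuous enrollment before and after the index date.* Alternatively, if earlier claims are available, keep the 1 March 2020 start, extend the data window for this analysis back to at least 7 March 2019, and state the same 360-day enrollment rule.

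The abstract says analyses were completed in 2024, so the sponsor should also record which cohort was actually used and re-run this analysis if the windows were truncated.

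The first option costs one sentence and a date and enrollment filter; launch-period patients are lost from this sensitivity analysis. The second keeps them but needs a wider data pull than the single extract described in section 8.6. Re-running the 180-day analysis in the restricted cohort would help separate the effect of window length from the change of cohort. It is an optional aid and not part of the correction.

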8.8. Quality Control

To ensure the highest standards of data quality and integrity, this study implements a comprehensive quality control framework, drawing on established procedures from both Pfizer's Real World Evidence (RWE) team and the IQVIA PharMetrics® Plus database.

Database Owner Procedures

IQVIA PharMetrics® Plus implements robust data quality assurance protocols, including standardized data collection, adjudication, and multi-step validation processes. Data are sourced from closed-network, third-party payers and are subjected to systematic checks for completeness, internal consistency, and plausibility before being released for research use. These processes are detailed in IQVIA's official documentation and have been described in peer-reviewed literature as industry standards for claims database management ^{40,41,50}.

Mechanisms to Ensure Data Quality and Integrity

The protocol will be interpreted by a primary statistical programmer with expertise in Real World Data (RWD). The primary programmer will develop working definitions for all study variables, outcomes, and subgroups in consultation with study investigators. The primary programmer will develop and execute a programming plan and share draft results with the study team as they become available.

The study team will provide feedback on draft results and discuss any unexpected, unclear, or contradictory findings until such issues are clarified or addressed by modifying methods and issuing updated draft results. Once the draft results are accepted by the study team, a secondary statistical programmer with expertise in RWD will perform quality control by reviewing all programs, related files (i.e., logs), and output developed by the primary programmer.

This review will first focus on identifying and addressing any errors in the program, related files, or output, and will then identify and address any issues in the interpretation of the protocol by the primary programmer. As needed, the secondary programmer may develop their own programs to run against the study database to replicate key findings (e.g., number of individuals who meet all eligibility criteria).

As needed, the study statistician may also review programs, related files, and output from the primary and secondary programmers to provide additional quality control.

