Variables: The primary exposure is initiation of rimegepant, defined by the first prescription fill between March 1, 2020, and October 1, 2022. Outcomes include changes in opioid and barbiturate utilization patterns before and after rimegepant initiation, measured by prescription fills, quantity dispensed, average dose, duration of use, and discontinuation. Key covariates are demographic and clinical characteristics (age, sex, region, comorbidities, chronic pain, prior preventive treatments) assessed during the baseline period.

Data sources: This study will analyze the IQVIA PharMetrics[®] Plus longitudinal health plan database, which includes anonymized, medical and pharmacy claims from closed-network, third-party payers in the US. This database includes commercial, managed Medicare, and managed Medicaid health plans.

Study size: The study database includes 52,591,063 individuals. It is estimated that 45,051 (0.86%) have an eligible first prescription for rimegepant and 4,049 (0.0077%) meet all eligibility criteria.

Data analysis: Number of fills and quantity dispensed (in MMEs for opioids and milligrams for barbiturates) will be assessed in the 180 days before and after the index fill for rimegepant. Changes in key outcomes will be analyzed using generalized linear mixed models adjusted for age, sex, region, chronic pain, comorbidities, and use of preventive treatment for migraine. Subgroup analyses will be conducted among individuals using ≥ 1 preventive treatment and individuals with problematic opioid use (≥ 3 fills or MMEs above 75th percentile).

Milestones: This study was initiated in 2023. Analyses were completed in 2024. A manuscript based on this study was accepted for publication in 2025.

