8.6. Data Management

All data for this study will be extracted from the IQVIA PharMetrics® Plus longitudinal health plan database. IQVIA is the data vendor and data store, providing access to a structured, de-identified dataset of adjudicated medical and pharmacy claims from a geographically representative sample of individuals with commercial, managed Medicare, or managed Medicaid health insurance in the United States.

Data will be obtained directly from IQVIA by Pfizer's Real World Evidence (RWE) team under an active data use license. The extraction process will follow Pfizer's standard operating procedures for secondary data studies. The RWE team will submit a formal data extraction request to IQVIA, specifying all required variables, inclusion and exclusion criteria, and the study timeframe. The data will be delivered in a secure, structured format (e.g., CSV or SAS datasets) and transferred to Pfizer's secure analytics environment for processing and analysis. The data extract will be limited to patients meeting the study's inclusion and exclusion criteria (e.g., adults with a diagnosis of migraine, first prescription fill for rimegepant between March 1, 2020, and October 1, 2022, continuous enrollment, etc.) and will occur once.

The technical specifications for the data extract—including all variable definitions, coding, and inclusion/exclusion parameters—are detailed in the study's data dictionary (see ANNEX 1. LIST OF STANDALONE DOCUMENTS). It provides detailed definitions, coding algorithms, and operational logic for all variables, exposures, outcomes, and covariates used in the study. This includes:

- Demographics: Definitions and coding for age, sex, and region.
- Comorbidities: Algorithms and ICD-10 codes for identifying chronic pain, migraine, and other relevant conditions.
- Medication Exposures: Lists of generic names, NDC/HCPCS codes, and logic for identifying study medications (e.g., opioids, barbiturates, migraine preventives, rescue inhalers, statins).
- Surgical and Injury Variables: CPT and ICD-10 code mappings for identifying major surgical procedures and injuries.
- Outcome Measures: Algorithms for calculating prescription fills, quantity dispensed, average dose (MME or mg), duration of use, and discontinuation.
- Operational Definitions: Clear instructions for how each variable is derived from claims data, including data sources (pharmacy or medical claims) and measurement periods.

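### Section 8.8 allows methods to be changed because draft results are unexpected, without separating error correction from result-driven change or requiring the latter to be labelled, and program review follows acceptance of the draft

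*Protocol*

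**What the plan says.** Protocol section 8.8 sets out the order of work.

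- Definitions: "The primary programmer will develop working definitions for all study variables, outcomes, and subgroups in consultation with study investigators". The same programmer runs the programs and shares drafts with the team as they become available.
- Feedback loop: the team is to "discuss any unexpected, unclear, or contradictory findings until such issues are clarified or addressed by modifying methods and issuing updated draft results".
- Review after the loop: "Once the draft results are accepted by the study team, a secondary statistical programmer with expertise in RWD will perform quality control". It looks first for errors in programs, related files and output, and "will then identify and address any issues in the interpretation of the protocol by the primary programmer".
- Optional checks: "As needed, the secondary programmer may develop their own programs to run against the study database to replicate key findings", with the count of eligible individuals as the example. "As needed, the study statistician may also review programs", related files and output.

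Two other parts of the protocol bear on this. Section 8.6 says of the data dictionary: "It provides detailed definitions, coding algorithms, and operational logic for all variables, exposures, outcomes, and covariates used in the study". On timing, the abstract (section 3) says: "Analyses were completed in 2024. A manuscript based on this study was accepted for publication in 2025". The protocol is version 1.0, dated 12 November 2025.

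**The concern.** Clarifying unclear output and correcting mistakes is ordinary quality control. Changing a method because its result was not the one expected is different: the choice of analysis then depends on the outcome. Section 8.8 puts both under one permission. The only end point it states for the loop is the team's acceptance of the draft.

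What counts as unexpected depends on what is anticipated, and here that is stated. The abstract's rationale says a migraine-specific treatment could lower opioid and barbiturate use. Section 6 cites an earlier analysis suggesting a decrease after starting such a treatment. Section 8.7.1 frames the models around reduction of other acute treatments. A null result, or a fall in one of the control drugs, could be treated as a finding to resolve. An error that produces the anticipated fall need not attract attention until the team has already accepted the draft.

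At stake is whether the reported pre/post changes can be read as results of a plan set in advance. If methods were changed in response to results and the change is not visible, the nominal p-values and intervals do not carry their usual guarantee.

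**Working it through.** The protocol gives no alpha, power or effect size on this point, so there is no figure to reproduce. The check is a reading of section 8.8 against the other sections.

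**Step 1: is the permission explicit?** Yes. Section 8.8 names modification of methods as one way to resolve an unexpected or contradictory finding. This is a stated rule, not a silence that another document could fill.

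**Step 2: is it limited?** Not in the protocol. Section 8.8 does not confine changes to errors and does not ask for a post hoc label or for the originally specified result to be shown alongside.

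**Step 3: what room is there to move?** Working definitions for all variables, outcomes and subgroups are set by the primary programmer with the investigators. Section 8.7.1 also leaves the distribution and link function of four outcomes (fills, quantity, average dose, duration) to be chosen after looking at the data. That is normal practice by itself, but it adds flexibility inside the loop.

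**Step 4: what checks the loop?** The secondary programmer's review is mandatory and covers all programs and the interpretation of the protocol, but it comes after acceptance. Replication and the statistician's review are both optional.

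**Step 5: what do the dates show?**

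| Event | Date | Source |
|---|---|---|
| End of data collection | 04 September 2023 | Section 5 |
| Data dictionary V3, table shells V1 | 15 November 2023 | Annex 1 |
| Analyses completed | 2024 | Section 3 |
| Manuscript accepted | 2025 | Section 3 |
| Protocol version 1.0 | 12 November 2025 | Title page, section 3 |
| Registration planned | 15 December 2025 | Section 5 |
| Final study report planned | 01 March 2026 | Section 5 |

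The dictionary and table shells are dated 72 days after data collection ended (26 days left in September + 31 in October + 15 in November). They also precede the completion of analyses. They may therefore have been fixed before any outcome result was seen, but the protocol does not say so, and it does not say that they barred later changes. The protocol version itself came after the analyses, so its date cannot show which choices came first.

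**Result.** The permission and the review order are both in the text. The protocol does not state which definitions and model choices predate the results.

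**The case against.** The strongest case on the other side has five parts.

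1. *The trigger has no direction.* Unclear and contradictory findings can point either way, and an implausibly large fall is also unexpected. This stands. A reader might infer that only null results can be re-specified while an anticipated fall is left alone. Section 8.8 does not say that. The lean toward the anticipated result is a risk inferred from the stated rationale, not a written rule.

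2. *A mandatory review follows.* What the team accepts is a draft, and every program is then reviewed whatever the direction of the result. This stands as a partial safeguard. The review is aimed at errors and protocol interpretation, so it would not necessarily flag a deliberate change of method that the team had agreed. The text calls this programmer secondary and does not claim independence.

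3. *Change logging may sit elsewhere.* Section 8.8 draws on the sponsor's established procedures, and a separate analysis plan may exist. This stands against any claim that no record was kept. It does not remove the permission that section 8.8 grants.

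4. *Definitions were documented and the timing is disclosed.* The dictionary and shells are dated 2023, and the abstract gives the 2024 and 2025 milestones openly. This largely stands. The sequence is not hidden, and the absence of listed amendments is correct for a version 1.0. What is missing is a statement of what was fixed before results were seen.

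5. *The analyses are finished.* Reordering the review cannot change them. This stands and limits the remedy.

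**Conclusion.** The point holds as a governance weakness. Section 8.8 permits method changes prompted by unexpected or contradictory draft results, does not distinguish them from error correction, does not require them to be labelled, and places the program review after acceptance. Given the anticipated reduction, this creates a risk of drift toward it, and nominal error rates are not guaranteed.

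The risk cannot be sized from the document. A reader might try to compute an inflated false-positive rate by assuming a significance level and a number of independent re-runs. The protocol states neither, and re-runs on the same patients would be correlated, so any such figure would be invented. A reader might also infer that every pre/post test is invalid, or that drift took place. The protocol shows only that drift was possible. Discontinuation, moreover, is defined by post-index fills alone and is not a pre/post contrast.

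The conclusion rests on section 8.8 as written and on the stated expectation of a fall. It would weaken if the sponsor can show that the definitions and models were fixed before outcome results were seen and that later changes were confined to errors. This should be corrected, and most of the benefit now comes through disclosure.

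**What to change.** 1. **Section 8.8, changes.** Limit changes after draft results to documented programming or protocol-interpretation errors, whatever the direction of the result. Label any other change post hoc and report it beside the originally specified analysis where records allow.
2. **Section 8.8, order.** For any further analyses, complete the secondary programmer's review before results go to the study team.
3. **Protocol and final report.** State that version 1.0 was written after the analyses. Say which definitions and model choices were fixed before outcome results were seen, including whether data dictionary V3 and table shells V1 were. Label the rest post hoc.

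The cost is redrafted wording and a reconstruction of the change history from existing files, with no new data. Before-and-after results can be shown only where records survive; where they do not, the report should say so. The downside is that some analyses will carry a post hoc label. The final report is planned for 01 March 2026, and it is the natural place for the disclosure.
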